**Exclusion criterion:**

1. Current or planned treatment with another investigational drug or device, with the exception of rcPMP treatment, through Day -1

**Investigational product, dosage and mode of administration:**

ORGN001 is a synthetic form of cPMP. Patients will begin IV infusions of ORGN001 at the same dose as their current dose of rcPMP. After the first 2 months of treatment with ORGN001, if the patient's clinical, PK, and safety assessments permit (including the absence of signs and symptoms of drug-related toxicity), dosing with ORGN001 will increase every month [REDACTED] until either 1) Day 180, 2) the patient reaches a dose that is not tolerated, 3) the patient's exposure exceeds that of the no observed adverse effect level (NOAEL) AUC [REDACTED], or 4) the patient's exposure following dose escalation is predicted to exceed that of the NOAEL [REDACTED], whichever comes first. Unscheduled dose adjustments of ORGN001 are possible based on recommendation by the SRC. During the Extension Period, patients who were de-escalated from the final tolerated dose for reasons other than safety or PK considerations may be re-escalated up to their maximally tolerated dose. After dose escalation is complete, the patient can be returned to a prior dose based on the patient's clinical status at the discretion of the treating physician after consultation with the SRC. All doses will be administered by IV infusion at a rate of 1.5 mL/minute.

ORGN001 is supplied as a sterile, [REDACTED] white to slightly yellow lyophilized powder [REDACTED] to be reconstituted using sterile Water for Injection prior to administration.

**Duration of treatment:**

After a 3-week Screening Period, ORGN001 will be administered once daily during the 6-Month Initial Treatment Period, followed by daily treatment in the Extension Period.

**Reference therapy, dosage and mode of administration: None****Criteria for evaluation****Safety variables:**

Treatment-emergent AEs, SAEs, clinical findings from physical examination, clinically significant laboratory abnormalities (serum chemistry, hematology, urinalysis), changes from baseline in laboratory analyses, EEGs, or vital signs (heart rate, respiratory rate, blood pressure, temperature), concomitant medications/procedures

**Efficacy variables:**

Changes in urine and blood SSC levels (urine levels normalized to urinary creatinine), clinical findings from neurologic examination, motor and cognitive assessment results (Bayley-III, GMFCS -expanded and revised, WPPSI), incidence of seizures (if present), findings from neuroimaging (magnetic resonance imaging scan), growth parameters (body weight, body length, head circumference), changes in feeding patterns

**Pharmacokinetic variables:**

- Cmax, tmax, AUC, t1/2, and dose linearity

**Statistical methods:**

The statistical analysis of all safety and efficacy parameters will be conducted on all patients who receive at least 1 dose of ORGN001. All data collected in this study will be documented using summary tables, figures and patient data listings. For categorical variables, frequencies and percentages will be presented. For continuous variables, descriptive statistics (n, mean, median, standard deviation [SD], minimum, and maximum) will be presented.

**Safety:**

The incidence of treatment-emergent AEs and SAEs will be summarized by System Organ Class (SOC) and Preferred Term overall, by severity, and by relationship to study drug. Changes from baseline in vital signs, laboratory assessments (chemistry, hematology, and urinalysis) will be summarized. Shifts from baseline in laboratory assessments as well as physical examination findings will be summarized for the different time points.

**Efficacy:**

Changes from baseline in urine and blood SSC levels and percentage changes from baseline to the study time points will be summarized. Observed values and changes in Bayley-III cognitive, gross, fine motor scaled scores and cognitive and motor composite scores will be summarized. The frequency of seizures will be summarized. Shifts from baseline in clinical findings from neurologic examinations and neuroimaging findings will be presented for the different time points. Growth parameters (body weight, body length, and head circumference) will be converted to age-adjusted z-scores and summarized over time. Graphical displays will be presented as appropriate.

**Pharmacokinetics:**

Plasma concentration versus time profiles will be graphically summarized. Noncompartmental PK parameters such as  $C_{max}$ ,  $t_{max}$ , AUC, and  $t_{1/2}$  will be determined if possible, and, dose linearity will be explored. Plasma concentration and PK parameter summaries will include descriptive statistics, as appropriate. [REDACTED]

Additional details for statistical analyses will be described in the statistical analysis plan.

## SUMMARY OF CHANGES

Section	Description of Change
1.3 Risk/Benefit Assessment	Additional text:  “ In vitro and preclinical studies have identified that ORGN001 has phototoxic potential. Patients and caregivers are instructed to avoid direct sunlight and to use precautions when exposed to the sun. Protective measures include wearing of sunglasses, a hat, long sleeved shirts, long pants and the use of protective sunscreen.”

## LIST OF ABBREVIATIONS AND DEFINITIONS OF TERMS

The following abbreviations and specialist terms are used in this study protocol.

**Table 2: Abbreviations and Specialist Terms**

Abbreviation	Definition
 H NMR	Proton nuclear magnetic resonance spectroscopy
 C NMR	Carbon nuclear magnetic resonance spectroscopy
 P NMR	Phosphorous nuclear magnetic resonance spectroscopy
AE	Adverse event
Alexion	Alexion Pharma GmbH
AUC	Area under the plasma concentration-time curve
BP	Blood pressure
Bayley-III	Bayley Scales of Infant and Toddler Development-Third Edition
°C	Degrees Celsius
C max	Maximum observed plasma concentration
CNS	Central nervous system
Colbourne	Colbourne Pharmaceuticals GmbH
cPMP	Cyclic pyranopterin monophosphate
CRF	Case Report Form
CT	Computed tomography
CYP 450	Cytochrome P450
DMC	Data Monitoring Committee
EC	Ethics Committee
E. coli	Escherichia coli
eCRF	Electronic Case Report Form
EEG	Electroencephalogram
EMLA	Eutectic mixture of local anesthetics
EOI	End of infusion
EOS	End of study
FAS	Full Analysis Set
GCP	Good Clinical Practice
GMFCS	Gross Motor Function Classification System
GMP	Good Manufacturing Practice
GTP	Guanosine triphosphate
IB	Investigator's Brochure
ICF	Informed Consent Form
ICH	International Council for Harmonisation
IEC	Independent Ethics Committee
INR	International normalized ratio
IRB	Institutional Review Board
IV	Intravenous
LC-MS/MS	Liquid chromatography with tandem mass spectrometric detection
MoCD	Molybdenum cofactor deficiency
MedDRA	Medical Dictionary for Regulatory Activities
MoCo	Molybdenum cofactor
MPT	Molybdopterin
MRI	Magnetic resonance imaging
MS	Mass spectroscopy
MSDS	Material Safety Data Sheet
N	Normal
NOAEL	No observed adverse effect level
Origin	Origin Biosciences, Inc.
PD	Pharmacodynamics

PI	Principal Investigator
PK	Pharmacokinetics
PT	Prothrombin time
RBC	Red blood cell
rcPMP	Recombinant E. coli -derived cPMP
SAE	Serious adverse event
SAP	Statistical analysis plan
SD	Standard deviation
SO	Sulfite oxidase
SOC	System Organ Class
SRC	Safety Review Committee
SSC	S-sulfocysteine
$t_{1/2}$	Terminal half-life
$t_{max}$	Time to maximum observed plasma concentration
UK	United Kingdom
US	United States (of America)
UV	Ultraviolet (spectroscopy)
WBC	White blood cell
WHODrug	World Health Organization Drug Dictionary
WPPSI	Wechsler Preschool and Primary Scale of Intelligence

# 1 INTRODUCTION

## 1.1 Background

Molybdenum cofactor deficiency (MoCD) is a rare, life-threatening, autosomal recessive, inborn error of metabolism characterized by disruption of the metabolic pathway for production of molybdenum cofactor (MoCo), which is essential for the function of sulfite oxidase (SO), xanthine dehydrogenase, and aldehyde oxidase. While all 3 enzymes are dependent on MoCo, the loss of SO activity is responsible for the severe and rapidly progressive neurologic damage seen in MoCD.

The incidence of MoCD is estimated to be between 1/100,000 and 1/200,000 newborn babies worldwide ([Schwahn 2015](#)). Affected individuals usually present in the neonatal period with intractable seizures, burst-suppression or multifocal epileptic electroencephalogram (EEG), exaggerated startle reactions, axial hypotonia, limb hypertonia, and feeding difficulties ([Johnson and Duran 2001](#); [Kikuchi et al, 2012](#); [Vijayakumr et al, 2011](#)). Neuronal injury is severe and is rapidly progressive as a result of accumulation of toxic levels of sulfite in the brain and subsequent formation of S-sulfocysteine (SSC). Death commonly occurs in the neonatal period, and patients who survive that period develop a severe static encephalopathy and developmental delay due to central nervous system (CNS) injury including subcortical cystic cavitation, hydrocephalus, diffuse cortical atrophy, and basal ganglia injury ([Johnson and Duran 2001](#); [Johnson et al, 1980](#)).

Three types of MoCD have been described based on the genetic defect. Two-thirds of MoCD patients have Type A, which is due to a mutation in the MOCS1 gene localized on 6p21.3 and results in the interruption of the first of the 4 synthetic steps in the formation of MoCo; guanosine triphosphate (GTP) cannot be converted into cyclic pyranopterin monophosphate (cPMP). Diagnosis of MoCD Type A is based on clinical presentation (encephalopathy, seizures) and biochemical phenotype (elevated urinary sulfite and SSC, and low or absent uric acid in the urine or plasma). The diagnosis is then confirmed by genetic testing. At present, there is no approved therapy available and no cure.

A treatment targeting MoCo biosynthesis represents a possible therapeutic strategy to treat MoCD Type A. A cPMP substitution therapy is expected to reconstitute MoCo biosynthesis and restore SO levels, thereby reducing the levels of the neurotoxic compounds, sulfite and SSC.

## 1.2 Rationale for the Study

The previous sponsor, Alexion Pharma GmbH (Alexion) developed ORGN001 (formerly ALXN1101), a synthetic form of cPMP, which is a precursor molecule to MoCo, as a treatment for MoCD Type A. Responsibility for the development of ORGN001 for the treatment of MoCD Type A has been assumed by Origin Biosciences, Inc. ORGN001 provides a therapeutic approach for the treatment of MoCD Type A that is intended to restore MoCo biosynthesis. Results of preclinical pharmacology studies with ORGN001 suggest that the metabolic derangement in MoCD Type A could be corrected by administration of synthetic cPMP, resulting in restoration of enzymatic activity and thereby correction of the metabolic pathways that lead to the accumulation of toxic metabolites causing CNS injury.

In vitro, ORGN001 increased molybdopterin (MPT) synthesis and restored SO activity ([Clinch et al, 2013](#)). Additionally, in a mouse model of MoCD Type A ([Lee et al, 2002](#)), ORGN001 effectively rescued MOCS1-/- mice from premature death and effectively decreased the plasma SSC level. In ██████████ repeat dose-toxicity studies in adult rats and dogs, ORGN001

did not accumulate and had a short (<1 hour) half-life. ORGN001 was well tolerated and did not show evidence of toxicity at the highest possible dose tested [REDACTED]. In a [REDACTED] juvenile rat study, ORGN001 was also well tolerated [REDACTED]. ORGN001 did not show any genetic toxicity. ORGN001 produced no effects on the cardiovascular, neurobehavioral, or pulmonary functions at the doses tested. [REDACTED]

The use of ORGN001 as a potential treatment for MoCD Type A is supported by preliminary clinical evidence obtained from MoCD pediatric patients treated with a recombinant *Escherichia coli* (*E. coli*)-derived cPMP product (rcPMP) from Colbourne Pharmaceuticals GmbH (Colbourne), [REDACTED]

[REDACTED] Published individual case reports suggest that intravenous (IV) administration of rcPMP may restore MoCo-dependent enzyme activities, as evidenced by reduction in the expression of biomarkers of the disease. Highly elevated urinary SSC values observed before initiation of treatment were corrected with rcPMP substitution. rcPMP substitution also resulted in improved neurologic outcomes for patients with MoCD Type A (Veldman et al, 2010; Veldman et al, 2011; Schwahn et al, 2011; Hitzert et al, 2012). The safety data related to these patients from the published literature indicated that the rcPMP infusions were well tolerated. No serious drug-related adverse events (AEs) were reported.

[REDACTED] This study aims to administer a GMP product, ORGN001, in a controlled setting to eligible patients identified as currently treated with rcPMP [REDACTED]. The study is designed to evaluate the safety and efficacy of ORGN001 after 6 months of treatment in patients with MoCD Type A who are currently treated with rcPMP. In addition, dose escalation will be performed to determine the starting dose for future studies.

The molecular structures of rcPMP and ORGN001 were compared using multiple spectral techniques [REDACTED] as well as in vitro efficacy assays, and it has been established that rcPMP and ORGN001 have identical core structures. The identical chemical structures of ORGN001 and rcPMP, together with the nonclinical results obtained with ORGN001 and clinical data obtained in pediatric MoCD Type A patients treated with rcPMP support the use of ORGN001 as a treatment for MoCD Type A. ORGN001 is expected to restore enzymatic activity and correct the metabolic derangement, as evidenced by the reduction in biomarkers of the disease, and thus, prevent the neurologic damage observed in MoCD Type A.

### 1.3 Risk/Benefit Assessment

MoCD Type A is a rare, life-threatening, autosomal recessive, inborn error of metabolism. Within a few hours to days after birth, newborn infants with MoCD Type A present a severe clinical picture with profound and progressive neuronal damage. Death commonly occurs in the neonatal period. Currently, no approved therapy is available for the treatment of patients with MoCD Type A. Treatment strategies for individuals with this disorder are only symptomatic and aim to provide relief of clinical manifestations of the disease and palliative care of the patient. Because of the life-threatening and debilitating nature of the disease and lack of treatment, there is a significant need to provide safe and effective treatment for pediatric patients with MoCD Type A, which targets the underlying cause of the disease, the inability to synthesize MoCo from

its precursor, GTP. Treatments that aim to restore MoCo biosynthesis, such as ORGN001, represent one of the most promising therapeutic interventions.

Considering the identical molecular structures of ORGN001 and rcPMP, the clinical results reported with rcPMP, and the nonclinical results with ORGN001, it is anticipated that ORGN001 will benefit patients with MoCD Type A by correcting the metabolic derangement, reconstituting the synthesis of MoCo, and thereby restoring SO enzymatic activity and reducing the levels of the toxic metabolites, sulfite and SSC.

*In vitro* and preclinical studies have identified that ORGN001 has phototoxic potential. Patients and caregivers are instructed to avoid direct sunlight and to use precautions when exposed to the sun. Protective measures include wearing of sunglasses, a hat, long sleeved shirts, long pants and the use of protective sunscreen.

#### 1.4 Rationale for the Patient Population

The patient population for this study includes the MoCD Type A patients who are currently treated with rcPMP [REDACTED]. Age at enrollment thereby depends on the age of patients currently treated with rcPMP.

#### 1.5 Rationale for Proposed Dosing

Patients will receive IV infusions of ORGN001 at the same dose as their current dose of rcPMP administered at a rate of 1.5 mL/minute.

ORGN001 drug product has been developed for IV use. Administration via the parenteral route is one of the best options because it provides rapid and consistent onset of action necessary for treatment of MoCD patients. Furthermore, the dose is easy to adapt to body weight, allowing greater dosing accuracy and more flexibility in case an adjustment of the dose is required.

The proposed starting doses are based on the safety and clinical effects reported with rcPMP. The dosing regimen in patients currently treated with rcPMP has been guided by clinical improvement and urine levels of SSC and thiosulfate (Veldman et al, 2010; Veldman et al, 2011; Schwahn et al, 2011; Hitzert et al, 2012). ORGN001 is expected to have similar pharmacodynamic (PD) effects since comparable activities on SO reconstitution and MPT restoration were reported with ORGN001 and rcPMP *in vitro* (Clinch et al, 2013). [REDACTED]

Based on the above observations, a dose-escalation scheme will be implemented in this study. Patients will start ORGN001 IV infusions at the same dose level as their current dose of rcPMP. The starting dose will be maintained for 2 months. After the first 2 months of treatment with ORGN001, if the patient's clinical, PK, and safety assessments permit (including the absence of signs and symptoms of drug-related toxicity), dosing with ORGN001 will increase every month [REDACTED] until either 1) Day 180, 2) the patient reaches a dose that is not tolerated, 3) the patient's exposure exceeds that of the no observed adverse effect level (NOAEL) AUC [REDACTED], or 4) the patient's exposure following dose escalation is predicted to exceed that of the NOAEL [REDACTED], whichever comes first. During the

Extension Period, patients who were de-escalated from the final tolerated dose for reasons other than safety or PK considerations may be re-escalated up to their maximally tolerated dose.

### 1.6 Rationale for the Overall Design

This is a Phase 2, noncomparative, open-label, multicenter, dose-escalation study to assess the safety and efficacy of ORGN001 in pediatric patients with MoCD Type A currently treated with rcPMP.

A placebo-controlled study would not be appropriate due to the severity of the untreated disease and the reported improved outcomes of MoCD Type A newborn infants treated with rcPMP. An active-comparator study is not feasible due to the lack of an approved treatment for MoCD Type A. This study aims to administer a GMP product in a controlled setting to patients currently treated [REDACTED].

Although this is an open-label study, the design still permits assessment of efficacy since the clinical outcome of untreated patients is well described. It is anticipated that as patients transition to ORGN001, they will have no change in their clinical status, thereby demonstrating comparable efficacy to rcPMP. The safety of ORGN001 will be reviewed continuously on an individual basis, as well as at a group level. A Safety Review Committee (SRC) [REDACTED] will review all available safety, efficacy, and if available, PK data on an ongoing basis.

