## **13 STATISTICAL METHODS AND PLANNED ANALYSES**

### **13.1 General Considerations**

Data collected during the study will be presented in summary tables, figures, or by-patient data listings. Continuous variables will be summarized using mean, standard deviation (SD), median, minimum, and maximum. Categorical variables will be summarized using percentages and frequency distributions. No formal hypothesis testing will be performed.

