#### **13.7.1 Primary Efficacy Analysis**

There is no prespecified primary efficacy endpoint in this study. Secondary efficacy analyses are described in [Section 13.7.2](#) [REDACTED].

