6.2.1.4. Hypothesis Testing and Significance Level

No statistical hypothesis testing will be performed. Efficacy data will be analyzed using descriptive statistics.

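### Protocol 1.6 reads a lack of change after the switch as demonstrating efficacy comparable to rcPMP, which this small descriptive design with conditional dose increases after Month 2 cannot show

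*Protocol*

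**What the plan says.** Protocol 1.6 gives two reasons why efficacy can be read from an open-label study. One is that "the design still permits assessment of efficacy since the clinical outcome of untreated patients is well described". The other concerns patients moving from rcPMP to ORGN001, of whom it anticipates that "they will have no change in their clinical status, thereby demonstrating comparable efficacy to rcPMP". The same section states: "This is a Phase 2, noncomparative, open-label, multicenter, dose-escalation study". The Synopsis entry is "Reference therapy, dosage and mode of administration: None".

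The analysis plan is descriptive:

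- Protocol 13.7.1: "There is no prespecified primary efficacy endpoint in this study".
- Protocol 13.1: "No formal hypothesis testing will be performed".
- SAP 6.2.1.4: "No statistical hypothesis testing will be performed. Efficacy data will be analyzed using descriptive statistics".
- SAP 6.2.1.5 plans no sensitivity analyses, and SAP 6.2.3 marks other efficacy analyses as not applicable.
- Protocol 13.2 enrols at least 4 patients; the final number depends on how many eligible rcPMP-treated patients there are.

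On dose, ORGN001 starts at each patient's rcPMP dose, and Protocol 1.5 adds: "The starting dose will be maintained for 2 months". Monthly increases then follow, up to Day 180, if clinical, PK and safety assessments permit. Protocol 3.3 and 3.4.2 also allow a reduction during the first 2 months.

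**The concern.** The second statement in 1.6 goes beyond describing patients. It says what a stable result would prove. Comparable efficacy is an equivalence-type conclusion, and absence of an observed change in a handful of patients does not establish it without a margin, a named endpoint and a statement of precision.

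The 6-month reading has a further problem. Protocol 1.2 frames the efficacy evaluation as being after 6 months of treatment, when many patients may be on more than their rcPMP dose. A product weaker than rcPMP at equal dose could look unchanged at Month 6 because the dose had been raised. Stable Month 6 results could then be reported as comparability between products when they reflect switch and escalation together.

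**Working it through.** The plan contains no power or precision figure to reproduce: no alpha, margin, effect size or SD is given. The steps below show what the stated design can support.

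**1. Precision of a mean change.** The 95% half-width, in units of the SD of within-patient change, is t(0.975, n−1)/√n.

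- n = 4 (Protocol 13.2 minimum): 3.182/2 = 1.59 SD.
- n = 6 (assumed): 2.571/2.449 = 1.05 SD.
- n = 8 (assumed): 2.365/2.828 = 0.84 SD.

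**2. No patient worsens.** For 0 of n, the exact upper limit on the true rate is 1 − a^(1/n).

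- n = 4, two-sided 95%: 1 − 0.025^(1/4) = 0.602, or 60%.
- n = 4, one-sided 95%: 1 − 0.05^(1/4) = 0.527, or 53%.
- If the true worsening rate were 20%, all four would still show no worsening with probability 0.8^4 = 0.41. At 30% it is 0.7^4 = 0.24.

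**3. Illustrative non-inferiority calculation.** This assumes a paired comparison, true change 0, one-sided alpha 0.025 and margins in SD units. None of these stands in the documents. The N column is the smallest number giving at least 80% power by the exact noncentral t.

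| Margin (SD) | N for 80% power | Power at n = 4 |
|---|---|---|
| 0.5 | 34 | 11% |
| 0.75 | 16 | 19% |
| 1.0 | 10 | 29% |
| 1.5 | 6 | 53% |

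**4. Time at the starting dose.** If the starting dose is kept for about 60 days, Days 61–180 are 120 of 180 days (67%) during which the dose may be above it. Monthly steps over those 120 days allow up to 120/30 = 4 increases. The four repeating three-visit cycles in the infusion row of Protocol Table 4 fit this, but the day headings are blank, so the count is an inference. Escalation is conditional, and some patients may have fewer increases or none.

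**5. Which planned summaries isolate the switch.**

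- Baseline is measured on rcPMP (Protocol 3.1 and 13.7.2, SAP 8.3), so change from baseline is a within-patient contrast with rcPMP.
- Protocol 3.3 collects PD samples about 3 days before each scheduled escalation and places a neurologic examination before the escalated dose is given.
- SAP 6.2.2.1 and 6.2.2.7 summarise neurologic findings and biomarkers by visit, and Protocol 13.7.2 adds individual SSC plots. A pre-escalation reading of both is therefore in the planned tables, but without a label or an interval.
- SAP 6.2.2.3 summarises seizures before treatment and over each 6-month period. The first period joins about 60 days at the starting dose to about 120 days of possible escalation, so this summary cannot isolate the switch.

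**6. The untreated reference.** Inclusion requires current rcPMP treatment (Protocol 4.2), while Protocol 1.1 describes death as common in the neonatal period. Enrolled patients are therefore survivors already carrying rcPMP's effect. The readable text names no external dataset or method.

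**The case against.** The strongest reply is that the sentence in 1.6 is an expectation in a rationale section. It is not a decision rule and makes no claim about Day 180. The study calls itself noncomparative, its primary objective is safety, and no objective asserts comparability. This stands as a limit on the consequence. It does not rescue the inference, because the wording still states what the expected result would demonstrate.

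Several stronger readings are tempting, and the documents do not support them:

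- A reader might infer that no planned analysis bears on the switch. By-visit change from an rcPMP baseline does, for SSC and neurologic findings.
- A reader might infer that the SAP never singles out the same-dose period. The visit windows and most appendices are blacked out, so a by-dose display there cannot be ruled out.
- A reader might equate the time before the first escalation with time at the rcPMP dose. Reductions are possible in the first 2 months, and a patient who never escalates, or who is returned to a prior dose, can be at the starting dose later.
- A reader might infer that an untreated contrast is planned. None is; 1.6 offers untreated outcome as context for having no control arm. For SSC, the level before any treatment has some value as context, because rcPMP stops before Day 1. The survivor problem applies most to survival and established CNS injury.
- A reader might take 1.59 SD to mean that a clinically large loss is compatible with stability. The documents give no SD, so the clinical size is unknown.

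It is also fair that a confidence interval from 4 patients adds little beyond individual plots. It is useful here only to display the imprecision.

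**Conclusion.** The point holds as a limit on what can be concluded about the switch. At the stated minimum of 4 patients, a stable result leaves a half-width of 1.59 SD for a mean change and an upper limit of 60% for the worsening rate. It cannot demonstrate comparable efficacy, and Month 6 adds the effect of any escalation. The half-widths assume roughly normal within-patient changes. The worsening limit assumes independent patients with a common rate.

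The gap in the analysis plan is narrower than the gap in the rationale. For SSC and neurologic findings, the early visits need to be named as the reading of the switch. For seizures, the only summary visible in the readable text pools the two phases. A reader might go further and conclude that the trial's efficacy data are uninterpretable or that its primary analysis is affected. Neither follows: within-patient description from an rcPMP baseline is sound, and the primary objective is safety.

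**What to change.** In SAP 6.2.2:

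- Prespecify, for each patient, the change from baseline to the last assessment before the first dose change of any kind, increase or reduction, for SSC, neurologic findings and seizures. State whether body-weight adjustments under Protocol 6.4 count as a dose change for this purpose.
- For SSC, show individual values, and the mean with a 95% CI labelled as descriptive.
- Split the first 6-month seizure summary at that point. Give rates per 30 days, because the two parts differ in length.
- Label later visits by whether the patient's dose differs from the starting dose.

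In Protocol 1.6, replace the closing claim of comparable efficacy with wording that describes clinical status after the switch. State that no formal comparison with untreated patients is made, since patients enter as survivors already treated with rcPMP.

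The cost is one added summary and a less favourable efficacy statement. The data come from visits, samples and diaries already planned, and no dosing rule changes.
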